5.2 Placebo

Participants randomized to the placebo arm will receive 0.9% sodium chloride. It will be matched in appearance, volume and administration to the active treatment arm with Tranexamic acid.

5.3 Drug Management

St. Jude Pharmaceutical Services Department is experienced with managing study drugs for clinical trials and will store and control Tranexamic acid and Placebo.

Drug Accountability Record Forms will be maintained to account for the inventory and disposition of the investigational agent including receipt, dispensing, returns and destruction. Participant specific doses will be ordered by investigators in the St Jude electronic medical record after enrollment. All doses will be dispensed from the SJCRH pharmacy with labels per our standard SOPs including at least participant name, medical record number, dose, and date. If a dose cannot be given, it should be returned to the SJCRH Pharmaceutical Services Department to be disposed with documentation.

To allow for the study team and participants to remain blinded to the treatment assignment, the study drug will be labeled as Tranexamic Acid/Placebo (TXAKIDS) followed by applicable dose and administration instructions.

6. REQUIRED EVALUATIONS, TESTS, AND OBSERVATIONS

6.1. Pre-Study Evaluations

All entry/eligibility studies must be performed within 1 week prior to entry onto the trial (unless otherwise specified).

Pre Study Evaluation – must be obtained before enrollment	Within 1 week of enrollment
History and physical exam with height (cm), weight (kg), and BSA	X
Laboratory Studies: CBC with Diff, CMP, Urinalysis, PT, PTT, fibrinogen, UA	X
Pregnancy test	Within 48 hours

6.2. Evaluations During Therapy

6.2.1 Intra-operative labs per Anesthesiology

- 6.2.1.1. ABGs q1 hour during the case (if arterial line present)
- 6.2.1.2. Intraoperative transfusion will occur for all patients with a Hb less than 8.0, and/or for patients with Hb between 8.0 and 9.0 AND a base deficit greater than or equal to -5. The transfusion dose will be 10 mL/kg for patients <30 kg and 1 full unit of packed red blood cells for patients >30 kg. A patient may receive multiple transfusions.
- 6.2.1.3. There may be a need for blood transfusion prior to Hb measurement in the setting of massive or brisk blood loss. This will be dictated by hemodynamic instability and/or obvious massive hemorrhage on the surgical field. Volume expanders other than packed red blood cells (i.e., Albumin) may be considered to allow time for Hb measurement and will be given at the discretion of the attending anesthesiologist.

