1. OBJECTIVES

1.1 Primary Objective

1.1.1. To evaluate the difference in intra-or post-operatively transfused blood volume (mL/kg) for patients undergoing limb salvage procedures of the distal femur or proximal tibia who are randomized to receive perioperative tranexamic acid (TXA) versus placebo.

- Study endpoint: intra- or post-operatively transfused blood volume (mL/kg), continuous measurement.

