6.2.4 CBC

6.2.5 Transfusions (intra-operatively and post-op)

- 6.2.5.1. Intra-operatively see 6.2.1.2.
- 6.2.5.2. Post-operative transfusion criteria
- 6.2.5.3. Hgb <7.0
- 6.2.5.4. Hgb <8.0 if unstable, tachycardic, or symptomatic, or at clinician's discretion
- 6.2.5.5. Volume of and number of patients receiving transfusion

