11. STATISTICAL CONSIDERATIONS

11.1 Sample Size Consideration and Randomization

This study will be conducted as a randomized, placebo-controlled double-blind trial of the administration of TXA vs. placebo prior to a limb salvage procedure. The primary objective will be to evaluate if TXA will reduce the proportional blood transfusion volume and EBL. The sample size is calculated based on the hypothesis that the TXA administration will reduce the average total volume of red blood cell transfused per kilogram of body weight by 40% relative to the average total volume of red blood cells transfused of the placebo group. Our historical data should be representative of our proposed placebo group, and historically, the average total red blood cell volume transfused per kilogram of body weight is $19.78 \text{ mL/kg} \pm 11.38$. The distribution of the intra-or post-operatively transfused blood volume is normally distributed after $\log(1+x)$ transformation (mean=2.906, sd = 0.507). We use the two-sample t-test with unequal variances to access the primary objective through the $\log(1+x)$ transformation of proportional blood transfusion volume.

We calculate the sample size with the two-sided two-sample t-test with unequal variances for the $\log(1+x)$ transformation proportional blood transfusion volume. Nineteen patients in each group are sufficient to detect a 40% decrease of $\log(1+x)$ transformation of proportional blood transfusion volume (mean=2.435, sd = 0.488) with 0.8 power and type I error 0.05. It can be safely assumed that the number of patients who

do not require blood transfusion is less than 5%. Given the sample size, we do not anticipate the blood transfusion volume will have substantial ties at 0.

Randomization will be performed in the SJCRH Pharmaceutical Services Department by a pharmacist using the randomization program developed by the Department of Biostatistics.²⁶ The drug is clear and will be given IV. The people who would determine the transfusion volume are blinded to the treatment. The randomization is stratified by the variable pre-operative weight that leads to two strata: pre-operative weight > 45.2 kg and pre-operative weight <=45.2 kg, where 45.2 kg is the median of pre-operative weight in the historical control data underwent limb-sparing tumor resections of the proximal tibia or distal femur. The assignment ratio of the TXA group to the placebo group is 1:1.

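### The base-deficit condition in the Hb 8.0–9.0 intra-operative transfusion tier (6.2.1.2) has a sign that does not fit its inequality, so neither formal reading singles out patients with a deficit of 5 or worse

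*Combined protocol and SAP*

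**What the plan says.** Section 6.2.1.2 sets two intra-operative triggers. The first rests on haemoglobin alone: "Intraoperative transfusion will occur for all patients with a Hb less than 8.0". The second covers a borderline haemoglobin and adds a condition; it applies "for patients with Hb between 8.0 and 9.0 AND a base deficit greater than or equal to -5". The dose follows in the same item: "The transfusion dose will be 10 mL/kg for patients <30 kg and 1 full unit of packed red blood cells for patients >30 kg". Repeat transfusions are allowed.

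The neighbouring items set the scope:

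- 6.2.1.1 schedules hourly arterial blood gases only where an arterial line is in place.
- 6.2.1.3 covers massive or brisk bleeding, where blood may be needed before a haemoglobin result is available.
- 6.2.5.1 adds nothing of its own on the intra-operative trigger: "Intra-operatively see 6.2.1.2".
- The post-operative criteria in 6.2.5 are Hgb below 7.0 alone, or "Hgb <8.0 if unstable, tachycardic, or symptomatic", or at the clinician's discretion.

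Section 1.1 defines what these rules feed: "Study endpoint: intra- or post-operatively transfused blood volume (mL/kg), continuous measurement". Section 11.1 adds: "The people who would determine the transfusion volume are blinded to the treatment".

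**The concern.** Joining a second condition to a borderline haemoglobin makes sense only if it narrows the tier to patients who are worse off. The post-operative rule is built this way: the lower threshold stands alone, and the higher one asks for a further sign of compromise or a clinician's judgement. The base-deficit condition in 6.2.1.2 evidently has the same purpose, but its minus sign and its direction do not fit together. A deficit is the negative of base excess, so a threshold of −5 on the deficit scale lies on the alkalotic side of zero.

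The item is an operative instruction, and the volume it calls for is counted in the primary endpoint. If staff follow the text, patients in this tier may receive blood that the rule was probably not meant to require. If staff resolve the text differently from one another, the trigger varies from case to case. A monitor also has no single rule against which to check compliance.

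**Working it through.** This is a check of logic. The plan gives no figure for this tier, so there is none to reproduce.

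**Inputs.** The condition is as worded in 6.2.1.2. Write BE for base excess and BD for base deficit, with BD = −BE. The plan states neither the sign convention nor the unit.

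**Readings.**

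- A, literal (the value is a deficit): BD ≥ −5, so −BE ≥ −5, so BE ≤ +5.
- B, signed (the value is a base excess): BE ≥ −5.
- C, inferred intent (a deficit of 5 or worse): BD ≥ 5, so BE ≤ −5. The informal reading, minus 5 or more negative, gives the same rule.

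**Is transfusion mandated at Hb 8.5?**

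| BE | BD | A: BE ≤ +5 | B: BE ≥ −5 | C: BE ≤ −5 |
|---|---|---|---|---|
| +6 | −6 | no | yes | no |
| +5 | −5 | yes | yes | no |
| +2 | −2 | yes | yes | no |
| 0 | 0 | yes | yes | no |
| −3 | 3 | yes | yes | no |
| −4.9 | 4.9 | yes | yes | no |
| −5 | 5 | yes | yes | yes |
| −5.1 | 5.1 | yes | no | yes |
| −8 | 8 | yes | no | yes |
| −12 | 12 | yes | no | yes |

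A includes every patient whom C includes, but also everyone with a smaller deficit, no deficit, or a base excess up to +5. It therefore hardly restricts the tier, and the two triggers together come close to Hb below 9.0. B agrees with C only at exactly −5; above that value it mandates transfusion where C does not, and below it the reverse. Neither A nor B singles out the patients in C.

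**Scope.** Only this tier is affected. The Hb < 8.0 trigger, 6.2.1.3 and the post-operative criteria do not use base deficit. Within the tier, the condition can be applied only when a blood gas is available, and gases are scheduled only with an arterial line.

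**Volume per decision.**

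- Below 30 kg, the documented dose is 10 mL/kg.
- Above 30 kg, the dose is one unit, whose volume the plan does not give. Assume 300 mL (range 250–350 mL). At 45.2 kg, the historical median weight used for stratification in 11.1, this is 300/45.2 = 6.6 mL/kg (250/45.2 = 5.5; 350/45.2 = 7.7).
- For scale, the historical mean in 11.1 is 19.78 mL/kg, and 6.6/19.78 is about one third.

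These are upper figures for the net effect. The endpoint accumulates over the intra- and post-operative period, so a unit given at Hb 8.0–9.0 may avert a later one.

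**The case against.** The strongest defence is that the instruction is written for anaesthetists, who will take a base deficit followed by a negative number to mean a deficit of magnitude 5 or more. Reading A makes the added condition nearly empty and reading B turns it round, so a specialist has reason to reject both. On this view the defect is editorial. Much of that stands: staff may already apply the probable intent, and correcting the text would then only bring it into line with practice. It does not make the wording correct, because the reader must discard what the sentence says to reach the rule.

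A reader might infer more than the documents support:

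- *That patients with a deficit of 5 or worse are missed under either reading.* Reading A includes all of them; its fault is that it includes nearly everyone else.
- *That reading B denies blood to the most acidotic patients.* The item says when transfusion takes place and does not forbid it otherwise. Below −5, reading B does not mandate transfusion. The Hb < 8.0 trigger and 6.2.1.3 still apply.
- *That the comparison between arms is biased.* The same rule applies in both arms, and those who determine transfusion volume are blinded.
- *That power is lost by a calculable amount.* The documents do not give the number of patients in the tier, their base-excess values, the trigger used in the historical series, or the net effect of an early unit on later transfusion. Neither the size nor the direction can be derived.

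**Conclusion.** The point holds as a wrong threshold in an operative rule. The sign and the inequality in 6.2.1.2 do not fit, nothing elsewhere in the document resolves them, and neither formal reading isolates the group that the condition was evidently meant to pick out. Following the text can lead to unneeded or inconsistent transfusion at Hb 8.0–9.0 in cases with a blood gas, and that volume enters the primary endpoint. The logic needs no numerical assumption beyond BD = −BE.

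Three things are inferred or assumed. The intended rule is inferred from the structure of the tier and from the post-operative criteria, and is nowhere stated. That few patients exceed a base excess of +5 is a clinical assumption, since no distribution is given. The 300 mL unit is assumed.

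The practical effect is unknown and probably modest. The correction should be made because the rule is mandatory and the change is trivial. The point gives no reason to doubt the planned 19 patients per group.

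**What to change.** In 6.2.1.2, replace the second condition of the Hb 8.0–9.0 tier with: **base deficit ≥ 5 mmol/L (base excess ≤ −5 mmol/L)**. Giving both forms removes any doubt about sign. The clinical team should confirm the threshold and the unit, since the plan gives no unit and mmol/L is assumed here. Section 6.2.5.1 refers back to this item and needs no separate change.

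The cost is a one-line protocol correction, with no extra tests, no extra patients and no change to the sample size.

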6.2.2 CMP

6.2.3 Estimated Blood Loss (EBL)

- 6.2.3.1. At conclusion of surgery
- 6.2.3.2. EBL measured using Neptune system and weight of surgical laps, calculated by Surgery, Anesthesia, and circulating nurse.

6.2.4 CBC

6.2.5 Transfusions (intra-operatively and post-op)

- 6.2.5.1. Intra-operatively see 6.2.1.2.
- 6.2.5.2. Post-operative transfusion criteria
- 6.2.5.3. Hgb <7.0
- 6.2.5.4. Hgb <8.0 if unstable, tachycardic, or symptomatic, or at clinician's discretion
- 6.2.5.5. Volume of and number of patients receiving transfusion

6.2.6 Post-op coags

6.2.7 ROTEM

6.2.8 Management of drain and drain output

- 6.2.8.1. Drain emptied and recorded at discharge from PACU
- 6.2.8.2. Measured and recorded when drainage collection system bag is full and/or every 8 hours.
- 6.2.8.3. Drains will be placed to Hemovac or Somavac collection system. "Wall suction" will not be utilized.
- 6.2.8.4. Daily measurement of drain output will be tabulated (over a 24 and 48-

hour period)

6.2.8.5. Negative pressure wound therapy (if used) “output” will be measured and recorded per routine.

6.2.8.6. Patient to remain on antibiotics while drain is in.

6.2.8.7. Drains will be pulled when output is 75 ml or less per 24- hour period

6.2.9 Incisional care

6.2.9.1. Wound care nursing will evaluate the incision at first dressing change and at the first post-operative visit then subsequent visits up to 12 weeks post-op.

6.2.9.2. Starting at the first post-op visit, high risk incisions (patients receiving neoadjuvant chemotherapy) will be monitored every 7-14 days up to 12 weeks post-op or completion of chemotherapy

6.2.10 Incisional healing

6.2.10.1. Presence or absence of dehiscence

6.2.10.2. Presence or absence of clinically significant hematoma

6.2.11 Functional Assessment

6.2.11.1. All patients enrolled on the study will receive a standard physical therapy evaluation at the same timepoints (with a window of +/- 2 weeks for all):

- weeks post-operatively
- 3 months post-operatively
- 6 months post-operatively

6.2.11.2 Additionally, during each physical therapy evaluation, participants will complete the FMA, PROMIS, and ROM assessment of the lower extremities.

6.2.11.3 See Appendix V.

Please see the table below for more detail and obtain other tests as needed for good patient care.

REQUIRED EVALUATIONS, TESTS, AND OBSERVATIONS

STUDIES TO BE OBTAINED	Pre-Op	In surgery/PACU/ Post-op	End of Study
History	X	with each outpatient visit	X
Physical Exam (Ht, Wt, BSA, VS, BMI)	X	with each outpatient visit	X
Type and screen	X		
CBC with differential, platelets	X	In PACU; daily while inpt; 1 week post-op	X
Urinalysis	X		
ROTEM		X In PACU	
Transfusions (amount in cc)		X	
Drain output (amount in cc)		X, daily until pulled	
Incisional healing (visualization)		X Post-op	X
Estimated Blood Loss		X At conclusion of surgery	
CMP	X	In surgery; daily while inpt; post-op day 3; 1 week post-op	X
Wound f/u		Daily until hospital discharge. At week 1 +/- 4 d for all pts; Every 10-14 days +/- 4 d for "high risk" participants; Every 7-10 days +/- 4 d for wounds undergoing active management of problems; At 6,12 weeks +/- 2 wks. for "low risk" participants; All pts. at 2 & 3 months +/- 3 wks.	X
PT, INR, PTT, fibrinogen	X	PACU; Inpt; 1 week post-op	X
Pregnancy Test*	X		
Physical therapy attendance	X	Inpt, 1, 2, 4 and 6 weeks post op +/- 2 wks; 2 and 3 mos. post op +/- 2 wks	X
Functional Mobility Assessment (FMA)		6 wks., 3 mos. post op +/- 2 wks	X
PROMIS	X	6 wks., 3 mos. post op +/- 2 wks	X
ROM	X	6 wks., 3 mos. post op +/- 2 wks	X

* The St. Jude IRB requires that a female patient of childbearing potential must have a negative pregnancy test as a condition of clinical research eligibility.

Obtain other studies as needed for good patient care. End of study for each participant will be after the 6-month evaluation (+/- 1 month) has been completed.

6.3 Response Evaluations

6.3.1. Wound care follow up to include photo documentation for anyone on chemotherapy or undergoing radiation therapy or who develops a wound problem.

6.3.2. For high risk participants who are not at SJ weekly, local wound care must be found. These individuals must provide SJ with photo documentation of wound care follow up.

6.3.3. Wound complications will be graded using CTC AE version 5.0.

6.4. Off-Study Evaluations

6.4.1. Wound evaluation

6.4.2. Functional assessment by physical therapy

6.5 Long-Term Follow-up Evaluations

None.

7. EVALUATION CRITERIA

7.1. Toxicity Evaluation Criteria

The Common Terminology Criteria for Adverse Events (CTCAE) Version 5.0 will be used for toxicity and performance reporting. A copy of CTCAE Version 5.0 can be downloaded from the CTEP home page

https://ctep.cancer.gov/protocoldevelopment/electronic_applications/docs/CTCAE_v5_Quick_Reference_8.5x11.pdf

8. CRITERIA FOR REMOVAL FROM PROTOCOL THERAPY AND OFF-STUDY CRITERIA

8.1. Off-study criteria

8.1.1. Death

8.1.2. Lost to follow-up

8.1.3. Request of the Patient/Parent

8.1.4. Completion of all study-related treatment and follow-up

8.1.5. Discretion of the study PI

8.1.6. Found after enrollment to be ineligible

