3.2. Exclusion Criteria

- 3.2.1. Participants whose limb salvage procedure may require significant manipulation of major blood vessels.
- 3.2.2. Participants with known bone marrow deficiency resulting in red blood cell deficiency (e.g. Diamond-Blackfan anemia)
- 3.2.3. Participants receiving erythropoietin-stimulating agents (e.g. epoetin alfa)
- 3.2.4. Participants with active hemorrhagic cystitis (e.g. alkylator-induced) with gross hematuria or >50 RBCs per high powered field on urinalysis
- 3.2.5. Participants actively receiving all-trans retinoic acid (ATRA) or isotretinoin (Accutane)
- 3.2.6. Participants with known allergies to antifibrinolytics
- 3.2.7. Participants with known hypercoagulopathies
- 3.2.8. Personal history of a thrombosis or active thrombus
- 3.2.9. Participants currently on anticoagulation medications (e.g. warfarin, enoxaparin)
- 3.2.10. Participants with a history of seizures. Patients with a history of febrile seizure are eligible.
- 3.2.11. Persisting toxicity related to other systemic therapies (e.g. chemotherapy) which constitutes an unacceptable safety risk based on the judgment of the PI and/or the primary treating physician
- 3.2.12. Female participants who are currently pregnant or actively breastfeeding.
- 3.2.13. Female participants who are currently receiving estrogen-based contraception therapy.
- 3.2.14. Inability or unwillingness of research participant or legal guardian/representative to give written informed consent.
- 3.2.15. Participants enrolled in another clinical trial utilizing an IND/IDE experimental therapy.
- 3.2.16. Participants with a history of CNS disease.
- 3.2.17. Participants with known bleeding disorder.
- 3.2.18. Participants with known platelet dysfunction.

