8.1.7. Seizure

8.2. Off-therapy criteria

8.2.1. Development of unacceptable toxicity during treatment:

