10.2 Study Monitoring

This study is considered high risk (HR-3) for monitoring purposes. Protocol and regulatory compliance, including essential regulatory documentation, will be assessed as well as the accuracy and completeness of all data points relating to the primary and secondary objectives semi-annually. If the study design has strata, accrual will be tracked continuously. The first two enrollees will be monitored and 15 % of the study enrollees thereafter, semi-annually.

The PI and study team are responsible for protocol and regulatory compliance, and for data accuracy and completeness. The study team will meet at appropriate intervals to review case histories or quality summaries on participants and retain copies of the minutes which are signed by the PI.

Clinical Trials Operations (CTO) will verify informed consent documentation and eligibility status on 100% of St. Jude participants within 5 working days of enrollment completion.

Overall study conduct, compliance with primary and secondary objectives, age of majority consenting, safety assessments and reporting, and the timeliness and accuracy of database entries are monitored routinely.

Study documents routinely monitored on selected participants include medical records, database entries, study worksheets, and case report forms. Study documents are monitored for participant status, demographics, staging, subgroup assignment, treatments, investigational drug accountability, evaluations, responses, participant protocol status, off-study and off-therapy criteria, and for all other specifics as detailed in a separate study-specific monitoring plan. The study-specific monitoring plan may be revised over time, to adapt monitoring frequency and/ or intensity to a changing environment when appropriate (for example: new safety signals; positive history of compliance; all participants are in long term follow-up; or the enrollment period has ended).

The recording and reporting of Adverse Events, Serious Adverse Events (SAEs), and Unanticipated Problems (UPs) to include type, grade, attribution, duration, timeliness and

appropriateness will be reviewed by the Monitor/ CRM. The CRM will generate a formal report which is shared with the Principal Investigator (PI), study team and the Internal Monitoring Committee (IMC).

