The patients who receive only one dose due to anaphylaxis (grade 3 or 4) or seizure will be removed from the evaluation of all objectives. The anticipated rate of each toxicity is about 1%. However, the descriptive statistics will be calculated for these patients who receive only one dose, e.g., adverse events and endpoints in all the objectives. The expected accrual number for our study will be 39 patients (to yield 38 evaluable subjects).

Unacceptable toxicities consist of acute kidney injury (defined by doubling of creatinine) or anaphylaxis (grade 3 or 4) or thrombotic event or seizure. The anticipated rate of each toxicity is about 1%. Thrombotic events occurring six weeks beyond the time of surgery will not be considered related to TXA administration. A heuristic approach is used to monitor each of the three toxicities in the TXA group. For each toxicity, starting from the 3rd patient, if the number of patients with any toxicity is equal to or larger than 3, the study accrual will be paused and amendments to the protocol will be discussed with the IRB. This monitoring rule yields the largest type-I error rate 0.044 when the 20th (one patient is removed due to not receiving the 2nd dose) patient show the toxicity (the 20th patient and any two previous patients in the TXA group).

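### Off-study criterion 8.1.6 makes no exception for dosed patients, so someone found ineligible after receiving TXA/placebo loses scheduled adverse event follow-up

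*Combined protocol and SAP*

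**What the plan says.** Section 8.1 of the protocol lists the off-study criteria. One is "Found after enrollment to be ineligible" (8.1.6), with no time limit and no distinction between dosed and undosed patients. Another in the same list is "Completion of all study-related treatment and follow-up" (8.1.4). A separate list, "8.2. Off-therapy criteria", covers stopping study drug; ineligibility is not on it.

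After a patient goes off study, section 6.4 lists a wound evaluation and "6.4.2. Functional assessment by physical therapy", and 6.5 plans nothing further. Section 9.1.2.5 has adverse events assessed at each study encounter, and Appendix I schedules this from PACU to 6 months.

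Section 10.2 has the trials office verify "eligibility status on 100% of St. Jude participants within 5 working days of enrollment completion". That deadline runs from enrollment and is not tied to the date of surgery. The exclusions in 3.2 include "Personal history of a thrombosis or active thrombus" (3.2.8), known hypercoagulopathy (3.2.7) and seizure history (3.2.10).

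Section 11.1 pauses accrual "if the number of patients with any toxicity is equal to or larger than 3" in the TXA group. It treats thrombosis as possibly drug-related up to six weeks after surgery.

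**The concern.** Taking an undosed ineligible patient off study is harmless. Once both doses have been given, six hours apart, going off study no longer limits exposure; it only ends observation. Some of the patients concerned would be ineligible because they carry a risk for one of the monitored toxicities, such as a previous clot or seizure. Section 4.4.1 already warns that clot risk in this population may be higher than in previous TXA studies.

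At stake is safety ascertainment. A thrombosis three weeks after surgery in such a patient would fall inside the plan's attribution window but outside any scheduled assessment. The pausing threshold is only three patients, so one event that nobody looks for can decide whether accrual pauses.

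**Working it through.** **1. Does off-study end follow-up?** Section 8.1.4 makes completed follow-up a reason for going off study, and stopping drug has its own list in 8.2. Off-study therefore means that follow-up is over, not only treatment. With 6.4, 6.5 and 9.1.2.5 as above, no adverse event assessment is scheduled afterwards.

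**2. Can ineligibility come to light after dosing?** Yes, though it should be uncommon. The check in 10.2 may fall before or after surgery. The pre-treatment re-check in section 3 is conditional and covers laboratory tests only, so it would not reveal a clotting or seizure history.

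**3. The plan's own toxicity figure.** Section 11.1 states a largest type I error of 0.044 at the 20th TXA patient. Inputs: n = 20, threshold 3, about 1% for each of four listed toxicities, summed to 4%.

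P(X ≥ 3) = 1 − [0.96^20 + 20(0.04)(0.96^19) + 190(0.04²)(0.96^18)] = 1 − [0.4420 + 0.3683 + 0.1458] = 0.0439.

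This reproduces 0.044. A single toxicity at 1% gives 0.0010, so the stated figure is for toxicities pooled.

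**4. Effect of one missed event.** Suppose one of the 20 TXA patients has a toxicity after removal. If it is counted, a pause needs at least 2 events among the other 19; if it is missed, at least 3. The true pooled rates below are assumptions, not figures from the documents.

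| Assumed true rate | Pause, event counted: P(X₁₉ ≥ 2) | Pause, event missed: P(X₁₉ ≥ 3) |
|---|---|---|
| 5% | 0.245 | 0.067 |
| 10% | 0.580 | 0.295 |
| 15% | 0.802 | 0.559 |
| 20% | 0.917 | 0.763 |

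These are conditional on such an event occurring. If instead one TXA patient drops from the count without regard to outcome, the chance of a pause at 10% goes from 0.323 (n = 20) to 0.295 (n = 19).

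**5. Power.** Inputs from 11.1 on the log(1+x) scale: placebo 2.906 (SD 0.507), TXA 2.435 (SD 0.488), two-sided 0.05, unequal-variance t-test.

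- At 19 per arm: SE = √(0.507²/19 + 0.488²/19) = 0.1614. Noncentrality = 0.471/0.1614 = 2.917. With 35.9 df the critical value is 2.028 and power is 0.810, consistent with the stated 0.8.
- Accrual is 39. One loss leaves 38, the planned evaluable number.
- Two losses leave 37: power is 0.799 (19 placebo, 18 TXA) or 0.798 (18 placebo, 19 TXA).
- Three losses leave 36: power is 0.788 at 18 per arm.

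**The case against.** The strongest reply is that few patients would be affected and that the plan already has safeguards. A signed eligibility checklist is reviewed before the consent form is generated (3.4), eligibility is discussed daily with the attending physician (3.5), and patients are enrolled while surgery is still being planned (3.3). The 10.2 check may therefore often precede dosing. Anaphylaxis and acute kidney injury would usually show during infusion or the inpatient stay. Seizure is itself an off-study reason ("8.1.7. Seizure"), a separate matter. A missed pause also needs a chain of events: a TXA patient, ineligibility found after dosing, a toxicity after removal, and that toxicity being the deciding one. All of this stands, and it limits the point to a small number of patients and mainly to thrombosis.

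Four stronger readings are tempting, and the documents do not support them:

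- *Toxicity counting stops for these patients.* The rule in 11.1 counts patients in the TXA group, and no text takes a dosed ineligible patient out of it. An event recorded before removal still counts.
- *The randomised outcome is lost.* Section 11.1 removes only one-dose patients with anaphylaxis or seizure from evaluation. Appendix VI schedules transfused volume at PACU and days 1–6, so the primary outcome may already be recorded. The plan is silent on how these patients are analysed; it does not exclude them.
- *Eligibility is checked again at semi-annual monitoring.* Section 10.2 names eligibility only in the five-day check; the semi-annual review refers to protocol compliance in general.
- *No later event can reach the record.* Reporting of unanticipated problems to the IRB (9.1.1), and of unanticipated fatal or life-threatening events possibly due to treatment (9.3.1), is not limited to on-study patients. Only the 15-day FDA text for other events carries that limit.

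**Conclusion.** The point holds as a gap in safety ascertainment. Followed as written, 8.1.6 leaves an exposed patient with no scheduled adverse event assessment for the rest of the six-week thrombosis window and the 6-month follow-up. This rests on reading off-study as the end of follow-up, which 8.1.4 and the separate off-therapy list support.

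The size depends on how often ineligibility is found after dosing, which the documents do not say. With no such patient the effect is zero. If one TXA patient's event is missed, the chance of a pause drops by between 0.15 (at an assumed 20% rate: 0.917 − 0.763) and 0.29 (at 10%: 0.580 − 0.295). The stated 0.044 and the 19 per arm are both unaffected. Power is not a reason for the change: even if removed patients were also dropped from the analysis, which no text requires, two losses from 39 would cost about 0.01. The change is worth making because it is cheap, not because many patients are expected to be affected.

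**What to change.** Limit 8.1.6 to patients found ineligible before the first dose of TXA/placebo. Add that a dosed patient later found ineligible:

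- is recorded as an eligibility deviation;
- stays in scheduled adverse event follow-up unless consent is withdrawn;
- counts in the 11.1 toxicity rule;
- is kept in the comparison in the arm to which they were randomised.

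The last two items need a sentence in 11.1 as well as the change to 8.1.6. Whether a remaining dose is given is a clinical matter that this change leaves alone. Correcting the seizure criterion (8.1.7) or the one-dose exclusion in 11.1 would not close this gap, because they concern different patients.

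The cost is a short amendment. Under Appendices III and IV the only research items are ROTEM in PACU and the study drug, so continued follow-up adds no research test. The small downside is that a few ineligible patients remain in the analysis set.
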